4.8 Treatment

- Radiofrequency Device Treatment:
 - The type of treatment will determine if gel should be applied to the skin prior to treatment. The gel is a conductive gel created for treatments that use radio frequency (RF) to ensure the proper connection between the hand piece and the skin.
 - A neutral pad will be used in accordance with the operator's manual for the device.
 - The hand piece, applicator or tip will be placed in contact with the skin.
 - The entire defined treatment area will then be treated by delivering energy to the skin.
 - The hand piece, number of passes and parameters used for the treatment will be determined by the Investigator.
 - Parameters may be adjusted throughout the treatment to increase subject comfort.
 - Contact cooling built into the 60mm handpiece may be used to increase subject comfort.
 - Nitronox may be used to increase subject comfort and will be determined by the Investigator.
- Procedural adverse events will be documented.
- Subjects will be asked to report the general level of treatment discomfort/pain on a scale of 0 (none) to 10 (maximum intolerable pain).
- Some subjects may have an incomplete response or no response by the end of the study. At the end of the study treatments using an FDA approved/cleared treatment method may be discussed with the subject and obtained at the cost of the subject.

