4.10 Follow Up

- Subjects will receive a phone call or attend a visit 2 days and/or 1-week post treatment to record side effects. If a side effect is tracked, the site will continue to call the subject until the event resolves. If deemed necessary by the investigator, the subject may attend an unscheduled visit for side effect assessment.
- The subject may return for a follow up visit at 30, 90 and 180 days post last treatment for side effect and efficacy assessments.
- The assessments listed in the schedule of activities and observations table (Section 4.13) will be performed at all follow up visits.
- Adverse events will be assessed at all follow up visits.

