4.13 Schedule of Activities and Observations

Procedure	Screening/ Pretreatment*	Visit 1-5: Treatment Visits	Visit 6: (optional) 2 Day Post Last Treatment Visit or Phone Call	Visit 7: 1 Week Post Treatment Visit or Phone Call	Visit 8: (optional) 30 Day Post Last Treatment Visit	Visit 9: (optional) 90 Day Post Last Treatment Visit	Visit 10: (optional) 180 Day Post Last Treatment Visit
Medical History	X						
Pregnancy Verification	X						
Informed Consent	X						
Treatment Discomfort/ Pain Evaluation		X					
Treatment		X					
Photographs	X	X	X	X	X	X	X
Subject Experience		X					
User Experience		X					
Diary***		X		X			
OCT***	X	X		X	X	X	
Ultrasound***	X	X		X	X	X	
Subject Satisfaction					X	X	X
Adverse Events Assessment **		X	X	X	X	X	X

* Screening/Pretreatment activities must be performed within 30 days prior to 1st treatment and may be performed on the same day as Visit 1.

** If deemed necessary by the investigator, the subject may attend an unscheduled visit for side effect assessment.

***Ultrasound (US), Optical Coherence Tomography (OCT), and the Diary are optional assessments.

The sponsor anticipates that all subjects can be enrolled within 6 months. The subject participation in this study will last approximately to 1-7 months. The total duration of this study is anticipated to last approximately two years.

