4.15 Adverse Event Assessment

Recording of adverse events will take place at all visits.

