9.0 ADVERSE REACTIONS DEFINITIONS AND REPORTING REQUIREMENTS

All adverse events that occur, starting from the time of the first treatment, will be recorded in the source documents.

Adverse Events occurring will be captured and followed until the condition resolves, stabilizes, is otherwise explained, or the subject is lost to follow-up. Subjects will be instructed that they may contact the Investigator at any time throughout the course of the study.

The Investigator and/or designated study staff will review each event and assess its relationship to the study device (not related, unlikely, possible, probable, and highly probable). The following definitions will be used for rating relationship to the device treatments:

- Not related – The event is clearly related to other factors such as the subject’s clinical state, therapeutic interventions, or concomitant medications administered to the subject.
- Unlikely – The event was most likely produced by other factors such as the subject’s clinical state, therapeutic interventions, or a concomitant medication administered to the subject; and does not follow a known response pattern to the investigational product.
- Possible – The event follows a reasonable temporal sequence from the time of investigational product administration; **and/or** follows a known response pattern to the study sampling sessions; **but** could have been produced by other factors such as the subject’s clinical state, therapeutic interventions, or concomitant medications administered to the subject.
- Probable – The event follows a reasonable temporal sequence from the time of investigational product administration; **and** follows a known response pattern to the investigational product; **and** cannot be reasonably explained by other factors such as the subject’s clinical state, therapeutic interventions, or concomitant medications administered to the subject.

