- Highly Probable – The event follows a reasonable temporal sequence from the time of investigational product administration; **and** follows a known response pattern to the investigational product; **and** cannot be reasonably explained by other factors such as the subject’s clinical state, therapeutic interventions, or concomitant medications administered to the subject; **and** either occurs immediately following investigational product administration, **or** improves on stopping the investigational product, **or** reappears on repeat exposure, **or** there is a positive reaction at the application site.

Each adverse event reported will be graded on a 3-point severity. Using the following definitions for rating severity will be used:

- Mild – easily tolerated, causing minimal discomfort, and not interfering with normal everyday activities.
- Moderate – sufficiently discomforting and may interfere with normal everyday activities.
- Severe – incapacitating and/or preventing normal everyday activities.

A Serious Adverse Event (SAE) is any adverse device experience that results in any of the following outcomes: death, a life-threatening adverse device experience, in-patient hospitalization or prolongation of hospitalization, a persistent or significant disability/incapacity, or a congenital anomaly/birth defect. Important medical events that may or may not result in death, be life-threatening, or require hospitalization may be considered a serious adverse device experience when, based upon appropriate medical judgment, they may jeopardize the subject or subject may require medical or surgical intervention to prevent one of the outcomes listed in this definition

If any of the above adverse events are serious as defined by the FDA Code of Federal Regulations (CFR), Title 21, special procedures will be followed. All serious adverse events will be reported within 24 hours of acknowledgment to the Sponsor whether or not the serious events are deemed sampling session-related. All serious event reporting will adhere to 21 CFR part 812 and the IRB will be notified accordingly.

The SAE information will be entered into the database and a desk copy of the complete SAE report will be submitted to the files.

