Adverse events, whether serious or non-serious, will be followed until the condition is resolved, stabilized, otherwise explained or the subject is lost to follow-up. Adverse events will be captured throughout the study and where appropriate, medical tests and examinations will be performed to document the resolution of event(s). Outcomes may be classified as resolved, improved, unchanged, worse, fatal, unknown or lost to follow-up. Following the resolution of any study-associated adverse events there will be no further adverse event reports for that subject.

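### The closing sentence of Section 9 ends adverse event reports for the subject rather than for the resolved event, contradicting the rules for capture and reporting throughout the study

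*Combined protocol and SAP*

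**What the plan says.** The last sentence of Section 9.0 reads: "Following the resolution of any study-associated adverse events there will be no further adverse event reports for that subject". Elsewhere the protocol says:

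- Section 9.0, opening: "All adverse events that occur, starting from the time of the first treatment, will be recorded in the source documents".
- Section 9.0, on serious events: "All serious adverse events will be reported within 24 hours of acknowledgment to the Sponsor". This holds whether or not the event is judged related, and no exception is made for a subject with an earlier, resolved event.
- Section 9.0, in the same paragraph as the closing sentence: "Adverse events will be captured throughout the study".
- Section 4.8 (treatment visits): "Procedural adverse events will be documented".
- Section 4.10 (follow-up): "Adverse events will be assessed at all follow up visits".
- Section 4.13: the row "Adverse Events Assessment" is marked for the treatment visits and every later contact.
- Section 4.15: "Recording of adverse events will take place at all visits".

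Section 4.16 adds that the sponsor or its designee reviews all documented events against regulatory reporting requirements. Sections 4.2 and 4.10 contain a stop of a different kind: calls about a side effect continue until that event has resolved.

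**The concern.** The closing sentence attaches the end of reporting to the person. The other provisions run to the end of participation or, in Sections 4.2 and 4.10, attach the stop to a single event. A site that follows the closing sentence literally would send no report of a new or recurrent event once an earlier study-associated event had resolved. A site that follows the rest of the protocol would.

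This touches a primary objective, since Section 4.1 makes the recording of side effects during the study the means of assessing safety. Treatment is repeated, so later sessions carry risk of their own. Section 9.0 counts reappearance on repeat exposure among the alternatives that can support its highest relatedness rating, and a recurrence after resolution is what the sentence would leave unreported. Section 9.0 also applies its three-point severity grade to each event reported, so an unreported event may have no grade. If centers follow different sentences, event figures will not be comparable across the 8 centers.

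**Working it through.** **Text comparison.** The protocol states no figure to reproduce, so the first check is whether any reasonable reading of the closing sentence removes the conflict.

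1. *The stop comes when the first study-associated event resolves.* This contradicts capture throughout the study, recording from first treatment and at all visits, and 24-hour reporting of serious events.
2. *The stop comes when all of the subject's current study-associated events have resolved.* A new event after a later treatment is still cut off, so the contradiction remains.
3. *Reports means only reports to the sponsor or IRB.* Recording in source continues, which eases the conflict with Sections 4.10 and 4.15 and the opening of Section 9.0. The conflict with the rule on serious events remains, and the sentence fits poorly with the sponsor's review of all documented events.
4. *Only follow-up of the resolved event is closed.* This removes the conflict, but it is not what the words say.

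**Timing.** Section 4.16 says mild swelling and redness typically resolve in 2 to 24 hours, and Section 4.2 allows up to 10 treatments. Under reading 1 the cut-off could therefore fall within a day of the first treatment.

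**Illustration of size under reading 1.** Inputs from the protocol: T = 10 treatments at most (Section 4.2), and T = 5 as a smaller course, matching the treatment visits shown in Section 4.13. Assumed, because the protocol gives neither an event rate nor a treatment interval: a probability p of a study-associated event per session, independent sessions, and each event resolved before the next session.

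- True episodes per subject = T × p
- Reported episodes per subject = 1 − (1 − p)^T
- Share unreported = 1 − reported / true

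| T | p | True | Reported | Unreported |
|---|---|---|---|---|
| 1 | any | p | p | 0% |
| 5 | 0.05 | 0.25 | 0.23 | 10% |
| 5 | 0.1 | 0.5 | 0.41 | 18% |
| 5 | 0.3 | 1.5 | 0.83 | 45% |
| 5 | 0.5 | 2.5 | 0.97 | 61% |
| 10 | 0.05 | 0.5 | 0.40 | 20% |
| 10 | 0.1 | 1.0 | 0.65 | 35% |
| 10 | 0.3 | 3.0 | 0.97 | 68% |
| 10 | 0.5 | 5.0 | 1.00 | 80% |

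The loss reaches half at p = 0.356 for T = 5 and at p = 0.168 for T = 10. The proportion of subjects with at least one event is 1 − (1 − p)^T with or without the stop, so it is unaffected.

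**Incidence of one event type.** Take a burn with an assumed probability q = 0.01 per session, counted within p.

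- True subject incidence = 1 − (1 − q)^T
- Reported subject incidence = (q / p) × [1 − (1 − p)^T], because only a burn in the subject's first event-bearing session is reported

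| T | True | Reported, p = 0.1 | p = 0.3 | p = 0.5 |
|---|---|---|---|---|
| 5 | 4.90% | 4.10% | 2.77% | 1.94% |
| 10 | 9.56% | 6.51% | 3.24% | 2.00% |

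Section 16.0 plans percentages of subjects within each category, so tables by event type and severity are the ones exposed.

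**The case against.** The best defense is that the sentence is a close-out rule. Its paragraph goes from follow-up to resolution, through capture during the study and classification of outcome, to the end of reporting. It speaks of events in the plural and never of a first event. Read that way, nothing is lost. Most of the provisions set against it concern recording, assessing or capturing rather than reporting. Section 4.16 accepts documentation in case report forms or source, Section 11.0 has the sponsor review case report forms and collect data at the end of follow-up, and Section 16.0 does not limit its tables to reported events. Later events may therefore still be counted. The percentages need the literal reading, sites that obey it over several other passages, and assumed rates. At p = 0.02 the same formula gives a loss of only about 4% (5 treatments) or 9% (10 treatments). An unresolved event, such as a scar or nodule, would delay or prevent the cut-off.

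Much of this stands. The benign intent is probable, source records may well hold later events, and the figures only illustrate. But the close-out reading has to be supplied by the reader, because the words name the subject and set no end-of-study condition. The distinction between recording and reporting does not rescue the sentence from the rule on serious events, which is itself a reporting rule. No passage sets precedence.

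**Conclusion.** The contradiction holds and should be fixed. It rests on the text alone: the closing sentence of Section 9.0 conflicts directly with the 24-hour rule for serious events and sits against the provisions for capture throughout the study.

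The practical size is uncertain. If the sentence is followed literally and the tables are built from reported events, event counts, rates per treatment, worst severity per subject and incidence by type are biased downward. The loss runs from nothing with a single treatment to most episodes when 10 treatments are combined with a high event rate per session. The any-event percentage is safe. How many treatments subjects typically receive, how often events occur, and which records feed the analysis are not stated, so no single figure for the loss can be given.

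**What to change.** Replace the closing sentence of Section 9.0 with wording such as: *Once an adverse event has resolved, no further follow-up reports are required for that event; new or recurrent events continue to be recorded and reported until the subject's last study contact.* This keeps the probable intent and agrees with the other provisions. Because the 30-, 90- and 180-day visits are optional, the last contact will differ between subjects; it is nevertheless consistent with capture throughout the study.

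The cost is one sentence in an amendment, with IRB approval as Section 20.0 requires, and a memo to sites. No visits are added. No change to case report forms or database should be needed, since recording at all visits is already required, but the forms are not in the documents and this should be confirmed. The reported adverse event rate may rise.

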10.0 PROTOCOL DEVIATIONS

All requests for protocol deviations by the Investigator have to be communicated to the sponsor in writing and if accepted by the Sponsor must be approved by the IRB. If a deviation occurs, the Investigator must inform the Sponsor as soon as possible. The Sponsor will notify the IRB in accordance with IRB specific policies.

11.0. DATA RECORDING, COLLECTION AND MONITORING

The sponsor will train the site and may be present at initiation of treatment. The sponsor will also monitor the site periodically. The sponsor may request intermediate data following each visit to evaluate treatment progress. Case Report Forms will be reviewed for current data and Regulatory Binders will also be reviewed for correct documents. The sponsor will collect data at the end of the follow up period. The sponsor will list the study on clinicaltrials.gov as required by FDA regulations.

12.0 CONFIDENTIALITY AND DISCLOSURE OF MEDICAL INFORMATION

As part of this study the Investigator and the team at the study center will keep records of subject participation in the study. These study records will include personal information that the subjects provide including age, sex, etc., the results of the study, information about response to treatments,

photographs taken during the study and other medical information relating to participation in the study.

Under federal law the study records cannot be used or disclosed by the Investigator for research purposes unless subjects sign the informed consent authorization.

Some or all of the test results, photographs and other information will be reported to Cynosure, Inc. the manufacturer of the device (Sponsor), and consultants that are helping conduct the study. The Sponsor and its consultants will analyze and evaluate these results and information and may report them to the U.S. Food Administration and the FDA, Institutional Review Board or other regulatory agencies in the United States and/or foreign countries. The subject's study records will be assigned a code number by the study team and they will ordinarily not be identified by name in the study records that are sent to the Sponsor and its consultants. However, The Sponsor, the Institutional Review Board and its consultants will have the right to see the complete study records, including the subject's name, and might choose to do so. If reports or articles are written about the study, the subject will not be identified by name in them however their photographs and study information may be used.

The study center will review and use the study records only for purposes of this study. They will keep the subject's identity confidential and, except for the disclosures described above, will not disclose the study records to other parties unless disclosure is required by law. Once the study center discloses information in the study records, photographs or medical records to the Sponsor or its consultants, the information will no longer be protected by federal law. Because of the need to release information to these parties, absolute confidentiality cannot be guaranteed. However, the Sponsor and its consultants will only use information for purposes of the study and will not disclose your study records to parties other than; the FDA or other regulatory agencies in the United States and/or foreign countries, unless disclosure is required by law. If reports or articles are written about the study, subjects will not be identified by name in them however their photographs and study information may be used.

Study records will be kept at the study center according to applicable regulations and policies and may be kept indefinitely following the completion of the study. Subjects will not have the right to review their records while the research is in progress. However, they will be able to review their records after the research has been completed.

13.0 LABELING

Sample labeling and directions for use are contained in the Operators Manual for the device.

14.0 CLINICAL RESEARCH CONDUCT

The study will be conducted in accordance with the protocol, International Conference on Harmonization (ICH) GCP guidelines, applicable regulations and guidelines governing clinical study conduct and ethical principles that have their origin in the Declaration of Helsinki. The investigator must ensure that the study is conducted in accordance with the provisions as stated in the FDA regulations and complies with the applicable local or regional regulatory requirements.

15.0 INFORMED CONSENT

During the screening, the investigator or a representative on their behalf will perform the informed consent process and discuss all aspects of the study. A signed informed consent form

(ICF) shall be obtained from the subject, clearly indicating his/her understanding of the study requirements, as well as the possible risks involved with study participation.

16.0 DATA ANALYSIS

All data will be analyzed at the end of the study. The primary analysis will be performed by the intention-to-treat approach. All subjects who begin the treatment is considered to be part of the study whether the subject completes the study or not. Additional per-protocol analysis may also be performed on subjects who complete the entire clinical trial according to the protocol. The most appropriate method of handling missing values will be chosen based on the particular trial's goals, endpoints and context.

Endpoints will be summarized with descriptive statistics. Continuous variables will be summarized with n, mean, standard deviation and range. Frequency counts and percentage of subjects within each category will be presented for categorical data. If applicable, Student's t-test may be used to determine if two sets of data are significantly different from each other and p-values will be reported. If the calculated p-value is below the threshold chosen for statistical significance (0.05, or 0.01 level) then the null hypothesis is rejected in favor of the alternative hypothesis. Subgroup analyses may be performed to identify a subject population that achieves the most benefit. Interim results may also be collected and reported as deemed necessary.

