4.0 PROTOCOL

4.1 Purpose and Objectives

The purpose of this study is to develop parameters and assess the safety of the radiofrequency device for a variety of treatments. Treatment results may also be evaluated.

The Primary Objectives are:

- To develop treatment parameters.
- Assess the safety through recording of side effects during course of study.

The Secondary Objectives are:

- Subject satisfaction via continuous verbal feedback during the procedure and at follow up visits.
- Assess the ease of use, patient response, treatment time, functions of the new device.

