4.2 Protocol Summary

Subjects are to be enrolled in this clinical study if they are 18 years of age or older. Up to 225 subjects will be enrolled at 8 study centers. All subjects may receive up to 10 treatments or multiple treatment areas. Subjects will receive a phone call or attend a visit at 2 days and/or 1 week post treatment to record side effects. If a side effect is tracked, the site will continue to call the subject until the event resolves. If deemed necessary by the investigator, the subject may attend an unscheduled visit for side effect assessment. The subject may return for optional follow up visits at 30, 90 and 180 days post last treatment for side effect and efficacy assessments.

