4.3 Protocol Study Design

This investigation is a multi-center, prospective, open label study.

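### Side-effect rates, a primary objective, are to be reported as counts and percentages with no confidence interval, so a zero or small count does not show what true rate remains possible

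*Combined protocol and SAP*

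**What the plan says.** Section 4.1 names two primary objectives: developing treatment parameters, and safety, worded as "Assess the safety through recording of side effects during course of study". Section 4.2 sets the size: "Up to 225 subjects will be enrolled at 8 study centers". Section 4.3 describes the design: "This investigation is a multi-center, prospective, open label study". No control arm is described.

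Section 16.0 is the only analysis text. Its general rule is "Endpoints will be summarized with descriptive statistics". For categorical data it adds "Frequency counts and percentage of subjects within each category will be presented for categorical data", and for continuous data "Continuous variables will be summarized with n, mean, standard deviation and range". The one inferential method is optional: "If applicable, Student's t-test may be used to determine if two sets of data are significantly different from each other and p-values will be reported". The analysis set is everyone who starts treatment, whether or not they complete the study.

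Under Section 9.0, adverse events are graded on a three-point severity scale and a five-level scale of relationship to the device. These are categorical data, so the rule on counts and percentages governs them.

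**The concern.** A percentage based on few events says little unless its precision is shown. Section 4.16 lists burns, scarring, infection and nodules among the anticipated effects, and the protocol gives no expected rate for any of them. If some prove uncommon, their table rows will show zero, one or two subjects. That is where the observed percentage is least informative about the true rate.

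The t-test does not fill the gap. It compares two sets of data, and it puts no bound on the proportion of subjects with a burn or a nodule in a study without a control group.

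The issue is sharper for the 60mm handpieces and flexible applicators, which Section 2.0 describes as not cleared by the FDA. Section 4.8 leaves the choice of handpiece to the investigator, so the number of subjects treated with each is not fixed in advance and may be well below the study total. A pooled percentage would not show how little is known about them.

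**Working it through.** **Stated figure.** There is none to reproduce. The 225 is a ceiling, and no expected rate, margin, power or precision target accompanies it.

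**Inputs from the protocol.** At most 225 subjects at 8 centers (Section 4.2); percentages on a per-subject basis, among those who start treatment (Section 16.0).

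**Assumptions.** Two-sided 95% confidence; subset sizes of 28 to 150; true rates of 0.1% to 2%. The size 28 is an equal share per center, 225/8 = 28.1. The protocol gives no number per handpiece.

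**Exact limits with no events.** The Clopper-Pearson two-sided 95% upper limit is 1 − 0.025^(1/n).
- n = 225: 1 − 0.025^(1/225) = 1.63%
- n = 150: 2.43%
- n = 100: 3.62%
- n = 50: 1 − 0.025^(1/50) = 7.11%
- n = 28: 12.34%

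**Exact limits with x events, x > 0.** The lower limit is the 0.025 quantile of Beta(x, n − x + 1), and the upper limit is the 0.975 quantile of Beta(x + 1, n − x).

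| Events/subjects | Percentage | Exact 95% interval |
|---|---|---|
| 1/225 | 0.44% | 0.01% to 2.45% |
| 2/225 | 0.89% | 0.11% to 3.17% |
| 3/225 | 1.33% | 0.28% to 3.85% |
| 5/225 | 2.22% | 0.73% to 5.11% |
| 1/50 | 2.00% | 0.05% to 10.65% |
| 2/50 | 4.00% | 0.49% to 13.71% |

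**Chance of seeing no event at all**, (1 − p)^n:
- n = 225: 0.999^225 = 79.8%; 0.995^225 = 32.4%; 0.99^225 = 10.4%; 0.98^225 = 1.1%
- n = 50: 0.99^50 = 60.5%; 0.98^50 = 36.4%

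So an effect with a true rate of 1% has about a one-in-ten chance of never appearing in 225 subjects. In a subset of 50 it would more often be missed than seen.

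**Sensitivity to the confidence level.** Section 16.0 does not fix a level for its tests: "threshold chosen for statistical significance (0.05, or 0.01 level"). For 0/225, a one-sided 95% limit is 1 − 0.05^(1/225) = 1.32%, and a two-sided 99% limit is 1 − 0.005^(1/225) = 2.33%. The conclusion does not depend on which is used.

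**The case against.** The strongest reply is that this is a descriptive, open-label study for developing parameters. It has no safety hypothesis, threshold or success criterion. Counts are reported beside percentages and the analysis set is defined, so a reader could compute the interval. Safety assessment is also more than a tally: Sections 4.16 and 9.0 provide for sponsor review, ratings of severity and relationship, and follow-up to resolution.

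Much of this stands. It limits the severity and rules out three stronger readings that a reader might infer.
- *That the sponsor will treat few events as proof of safety.* No section makes or plans that claim. Section 17.0 promises only a summary report of conduct and results.
- *That the effects at issue are serious events.* Section 4.16 lists burns, scarring, infection and nodules as anticipated side effects. Seriousness is defined separately in Section 9.0, by outcome.
- *That 1.6% is what the study will exclude.* That figure needs 225 treated subjects, but Section 4.2 gives a ceiling on enrolment and Section 4.6 counts a subject as enrolled at consent. It also averages over surgical and non-ablative uses and over cleared and uncleared applicators. It assumes that every event is seen, yet the 30-, 90- and 180-day visits are optional (Sections 4.2 and 4.13).

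The reply does not remove the point. An interval for a proportion is itself descriptive: it needs no hypothesis, power claim or extra subjects. Readers can compute it for a handpiece only if the treated denominator for that handpiece is reported, and Section 16.0 does not ask for one.

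**Conclusion.** The point holds as a reporting gap of modest severity. A primary objective is to be summarised with no measure of uncertainty. If few or no events of a given type occur, the planned tables will not show which true rates remain compatible with the data. Those rates run up to 1.63% for 0/225, and up to 7.1% for 0/50 if a handpiece were used in 50 subjects.

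The omission and the arithmetic are certain. The 95% level, the subset sizes and the illustrative true rates are assumptions. The limits treat subjects as independent and cover sampling error only. They do not allow for late effects missed because the later visits are optional, so for such effects the real uncertainty is wider than the interval.

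**What to change.** Add to Section 16.0 that each side-effect percentage (overall, by type, by severity and by device or handpiece) is reported with:
- the number of subjects actually treated, as denominator;
- an exact (Clopper-Pearson) two-sided 95% confidence interval, including the upper limit when no event is seen;
- the uncleared 60mm handpieces and flexible applicators shown separately.

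The subject should remain the unit, since one subject may have several treatments or areas.

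If a statement of precision is wanted in Section 4.2 or 16.0, it should be conditional. At best, with 225 treated, all uses pooled and follow-up complete, zero events excludes only rates above about 1.6%. The limit is higher for any single handpiece and does not cover late effects missed through the optional 30-, 90- and 180-day visits.

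The cost is a sentence or two and a few table columns, with no change to enrolment, treatment or visits. The site records must link each subject to the handpieces used. The downside for the sponsor is that the safety figures will look slightly less favourable.
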